The study will be conducted over 44 months. We expect to screen 70 atopic patients in order to enroll up to 50 suitable atopic participants to ensure randomisation of at least 44 atopic participants following their baseline visit. Additionally, we shall recruit 20 healthy, non-atopic volunteers. Individuals with severe grass pollen hay fever, with or without associated seasonal asthma, will be recruited and screened after the pollen season from December 2013 to April 2014. Atopic Participants will undergo baseline assessments in January to April 2014. Screening assessments will be completed before eligible participants are randomized to active or placebo treatment. Atopic participants will then begin AIT treatment in January-April 2014 and continue treatment for 12 months. All atopic participants will be provided with anti-allergic rescue medications (antihistamine tablets, topical intranasal corticosteroids, and eye-drops) throughout the pollen season. Clinical surrogate endpoint assessments, plus blood, nasal fluid and nasal brushing sampling, will be performed at baseline, at around 4, 8 and 12 weeks after starting the AIT, and during the peak pollen season, at 6 months and at 12 months of treatment. Nasal mucosal biopsies will be taken at baseline, around 5 months, and 12 months of treatment. After 12 months of treatment, unblinding will take place. Those atopic participants receiving active AIT treatment will continue therapy for another 12 months followed by a withdrawal phase of 12 months. At 24 and 36 months (visit 8 and

9) all procedures and laboratory markers that were performed at 12 months (visit 7) (Fig.1) will be repeated for atopic participants on active treatment. Those atopic participants on placebo will be offered 24 months of active treatment after unblinding.

The healthy, non-atopic participants will undergo screening and one visit only, at 12 months, to coincide with the 12 month visit for the atopic participants. This visit will include clinical surrogate endpoint assessments, plus blood, nasal fluid, nasal brushing sampling, and nasal biopsies. The assessments will serve as a control for the results of the atopic participants at 12 months.

Figure 1: Study plan, atopic participants

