6.5.10 Nasal epithelial brushings

Volunteers will undergo nasal brushings (either with Cyto-Soft Cytology Brushes or Rhinoprobes) on each side of the nose. This is a simple procedure and takes less than 5 minutes.

Materials

- Disposable non-latex gloves
- Tissues

- 5% lidocaine hydrochloride spray
- Cytology brush cutters, cleaned thoroughly with DNAZap™ solution before the procedure
- DNAZap™ (Applied Biosystems, Cat# AM9890)
- Sterile Cytosoft cytology brushes (Cyto-Soft Cytology Brush CYB-1. Cardinal Health #S7766-1A)
- Rhinoprobe curettes (Arlington Scientific, USA, curette 100 SY-96-0905)
- Nasal Epithelial Cell Collection Tubes with Media (RLT buffer +2-Mercaptoethanol (β -ME) Qiagen, West Sussex, UK)

Procedure

1. Explain procedure to patient.
2. Sit patient comfortably in a chair facing forward, with head tilted slightly back.
3. Apply local anaesthetic (5% lidocaine hydrochloride spray, 2-3 sprays per nostril) to both nostrils. Allow 2 minutes for onset of anaesthesia. (Procedure may be performed with or without local anaesthetic, according to participant preference, based on pilot studies currently in progress).
4. Give the participant a tissue for eye tearing or nose running.
5. If using Cytosoft cytology brushes: insert the cytology brush through the nasal vestibule medially along the floor of the nasal cavity and the septum, to the depth of the inferior turbinate.
6. Roll and move the brush laterally, under the inferior turbinate, to the anterolateral inferior turbinate. Rotate while moving the brush in and out, applying some pressure to the walls of the turbinate. Brush for 4 seconds.
7. Roll the brush away from the turbinate and remove from the nose.
8. Place the brush into a culture tube containing collection medium.
9. Gently agitate the brush in the culture medium for 4 seconds.
10. Cut the brush off at its handle so that it fits well in the tube.
11. Repeat if indicated.
12. If using Rhinoprobes: gently scrape the inferior turbinate twice, from posterior to anterior, remove Rhinoprobe from nose, insert cupped end into culture medium and agitate gently for 4 seconds.
13. Cap the tube and freeze at -80°C .

14. Check patient and offer further tissues if required.

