Table 2: Time line procedures at Visit 0b

Time (hr:min)	*Participants will be allowed to leave and return at 8hours	Procedure
00:00	Arrival	
00:15	Pre Lavage	Secretion collection
00:20	Nasal Lavage	Nasal lavage with 240 ml SinuRinse solution
00:25	Intradermal test	1BU intradermal inject to left and right forearm + saline injection
00:40	Intradermal test	EPR recorded at 15 minutes
00:50	Pre-Challenge	TNSS + VAS, PNIF, Secretion collection

00:55	Nasal Challenge	5,000 BU/ml Timothy grass pollen allergen
01:00	Early Nasal response	TNSS + VAS; PNIF; Secretion collection
01:10	Early Nasal response	TNSS + VAS; PNIF; Secretion collection
01:25	Early Nasal response	TNSS + VAS; PNIF; Secretion collection
01:55*	Early Nasal response	TNSS + VAS; PNIF; PeakFlow; Secretion collection
08:25*	Intradermal test	LPR
08:30		Secretion collection Nasal brushings Nasal biopsy

TNSS; total nasal symptom score

VAS; visual analogue scale

EPR; Early phase response

LPR; Late phase response

BU; Bioequivalent Unit

PNIF; Peak nasal inspiratory flow

Visit 1:

Initiation of treatment will take place after Visit 0 including an inspection of the nasal biopsy site. The patients will be required to remain for 60 minutes in the hospital after intake of the first AIT/Placebo.

Visit 2, 3 and 4:

After around 4, 8 and 12 weeks of treatment starting the tablets (AIT/placebo), participants will return during the morning for around 60 minutes to have a 120 ml blood sample taken. Furthermore the volunteers will fill out questionnaires and undergo nasal fluid collection and brushings. (see also **Table 3**)

Table 3: Time line procedures at Visit 2, 3 and 4

Time (Hr:min)		Procedure
00:00	Arrival	
00:05	Blood	Blood sample (120ml)
00:10	Questionnaires	mRQLQ, SMS, GE VAS
00:15	Pre-lavage	Secretion collection
00:20	Pre-lavage	Nasal brushings

00:25	Nasal-lavage	
00:55	Post-lavage	Secretion collection

GE VAS; Global Evaluation visual analogue scale

mRQLQ; miniRhinoconjunctivitis Quality of Life Questionnaire

SMS; Symptom Medication Score

At the start of May 2014, patients will receive the rescue medications (section 6.4.8.1) and will be asked to fill out the Global Evaluation (GE) VAS (**Appendix 4**), Symptom Medication Score (SMS) (**Appendix 5**) and mini-Rhinitis Quality of Life Questionnaire (mRQLQ) (**Appendix 3**) weekly until the end of July.

Visit 5:

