Around 5 months after begin of AIT/placebo and during the pollen season participants will come to the hospital for 1.5 hours. During this visit the following will be undertaken (see also **Table 4**):

- A period of 15 minutes acclimatization to hospital environment and relative inactivity.
- Participants will mark questionnaires (**Appendix 3-5**) corresponding to symptoms and rescue medication use during the current pollen season.
- Furthermore the volunteers will undergo the same procedures as in Visit 0b, plus questionnaires and with the exception of the intradermal skin test and nasal challenge.

Table 4: Time line procedures at Visit 5

Time (hr:min)		Procedure
00:00	Arrival	
00:05	Blood	Blood sample (200ml)
00:15	Pre-lavage	GE VAS; mRQLQ; SMS, secretion collection
00:20	Pre-lavage	Nasal brushing
00:25	Nasal-lavage	
00:55	Post-lavage	Secretion collection

		Nasal biopsy
--	--	--------------

GE VAS; Global Evaluation visual analogue scale

mRQLQ; mini Rhinitis Quality of Life Questionnaires

SMS; symptom medication score

Visit 6:

After 6 months of treatment and shortly after the pollen season patients will mark a retrospective GE VAS (scale 0-100 mm; **Appendix 1**), the mRQLQ (**Appendix 3**) and complete a retrospective GE chart (**Appendix 2**) documenting the overall severity of their hay fever symptoms during the previous pollen season. Also a nasal allergen challenge with 5.000 BU/ml Timothy grass pollen allergen will be undertaken. We will record the Peak Flow as well as the response to challenge for one hour at 5, 15, 30 and 60 min with TNSS + VAS and PNIF.

Time (hr:min)		Procedure
-00:15	Arrival	TNSS+VAS; GE VAS, mRQLQ, GE, PNIF; Peak Flow
00:00	Nasal Challenge	5,000 BU/ml Timothy grass pollen allergen
00:05	Early Nasal response	TNSS + VAS; PNIF
00:15	Early Nasal response	TNSS + VAS; PNIF
00:30	Early Nasal response	TNSS + VAS; PNIF
01:00	Early Nasal response	TNSS + VAS; PNIF; PeakFlow

Visit 7:

After 12 months on treatment volunteers will attend the allergy unit for a period of 2 hours in the morning and 1 hour during the evening (3 hours). During this visit the same procedures as described at Visit 0b plus a blood sample of 200 ml will be undertaken (see also **Table 2**).

Non-atopic Participants:

Scheduled Visits (screening (Visit -1), one time point assessment (Visit 1):

Screening Visit – September 1st to November 30th, 2014.

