- Peak nasal inspiratory flow (PNIF) will be assessed shortly before collecting the nasal fluid before the nasal challenge and after 5, 15, 30 and 60 minutes after the nasal challenge.
- Peak expiratory flow (Peak Flow) will be assessed before nasal allergen challenge and 60 minutes after nasal allergen challenge.
- Nasal fluid will be collected by inserting a single foam sponge into each nostril and will be left in place for 2 minutes before removal. Secretions will be collected before challenge, at 5, 15, 30 and 60 minutes after nasal challenge and after 8 hours.
- The volunteers are allowed to leave the hospital (e.g. for work) and will return in the evening (after 8 hours) to allow reading of the skin LPR. Additionally, volunteers will undergo nasal brushings on both sides and a nasal biopsy. After the biopsy, volunteers will be observed for a further 30 minutes to ensure there is no nasal bleeding, and then allowed home.

- Food and non-caffeine-containing beverages (at room temperature) will be provided to all participants.

Table 5: Time line procedures at Visit 1 for the non-atopic participants

Time (hr:min)	*Participants will be allowed to leave and return at 8hours	Procedure
00:00	Arrival	
00:10	Blood	Blood sample (200 ml)
00:15	Pre Lavage	Nasal secretion collection and brushing
00:20	Nasal Lavage	Nasal lavage with 240 ml SinuRinse solution
00:25	Intradermal test	1BU intradermal inject to left and right forearm + saline injection
00:40	Intradermal test	EPR recorded at 15 minutes
00:50	Pre-Challenge	TNSS + VAS, PNIF, Secretion collection
00:55	Nasal Challenge	5,000 BU/ml Timothy grass pollen allergen
01:00	Early Nasal response	TNSS + VAS; PNIF; Secretion collection
01:10	Early Nasal response	TNSS + VAS; PNIF; Secretion collection
01:25	Early Nasal response	TNSS + VAS; PNIF; Secretion collection
01:55*	Early Nasal response	TNSS + VAS; PNIF; PeakFlow; Secretion collection
08:25*	Intradermal test	LPR
08:30		Secretion collection Nasal brushings Nasal biopsy

TNSS; total nasal symptom score

VAS; visual analogue scale

EPR; Early phase response

LPR; Late phase response

BU; Bioequivalent Unit

PNIF; Peak nasal inspiratory flow

GE VAS; Global Evaluation visual analogue scale

mRQLQ; mini Rhinitis Quality of Life Questionnaires

SMS; symptom medication score

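### Protocol Table 5 puts a nasal brushing before the controls' nasal challenge that atopic Visit 7 and the control visit's own text do not have; the three need reconciling

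*Protocol*

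**What the plan says.** Three places in Protocol section 6.5.14 describe when noses are brushed on a challenge day.

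- **Controls, Table 5 (Visit 1).** The 00:15 pre-lavage row reads "Nasal secretion collection and brushing". Lavage with 240 ml follows at 00:20, pre-challenge TNSS, VAS, PNIF and secretion at 00:50, and the challenge with "5,000 BU/ml Timothy grass pollen allergen" at 00:55. A further brushing is listed with the biopsy at 08:30.
- **Controls, Visit 1 text.** The bullets that point to Table 5 mention brushing once, at the evening return: "Additionally, volunteers will undergo nasal brushings on both sides and a nasal biopsy".
- **Atopic participants, Visit 7.** The text says: "During this visit the same procedures as described at Visit 0b plus a blood sample of 200 ml will be undertaken". It refers to Table 2 ("Time line procedures at Visit 0b"), where the 00:15 row is secretion collection alone and brushing appears only at 08:30.

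Section 6.5.10 describes brushing as working the inferior turbinate with pressure, or scraping it. It includes the step "Apply local anaesthetic (5% lidocaine hydrochloride spray, 2-3 sprays per nostril) to both nostrils", qualified by "Procedure may be performed with or without local anaesthetic, according to participant preference".

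On the role of the controls, section 6 says: "The assessments will serve as a control for the results of the atopic participants at 12 months". SAP 7.2.1, 7.3 and 7.3.2 list a three-group comparison (active, placebo, non-atopic) for challenge TNSS, PNIF and the nasal-fluid markers.

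**The concern.** A control group read against the atopic arms at 12 months should reach the challenge by the same sequence of nasal steps. Under Table 5 it does not: the controls' mucosa has been brushed, and in some of them anaesthetised, before the pre-challenge reading. Brushing might irritate the mucosa and add secretions or mediators. Lidocaine might blunt itch and sneeze.

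The difference between groups would be systematic. Because lidocaine is the participant's choice, it would also vary within the control group. Neither document plans an adjustment for it.

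At stake is the control level against which a reader would judge whether treatment moves nasal measures towards normal. The serial nasal-fluid assays are the most exposed. SAP 7.3.2 plans tryptase at baseline, 5, 15, 30 and 60 minutes and 8 hours, and cytokines at baseline, 1 and 8 hours. If baseline there means the 00:50 sample, every point in both series comes after the extra brushing in controls.

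**Working it through.** The check is a row-by-row comparison of two tables and subtraction of clock times. There is no plan figure to reproduce.

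**Pre-challenge steps side by side**

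| Time | Controls, Table 5 | Atopic Visit 7, Table 2 |
|---|---|---|
| 00:15 | secretion and brushing | secretion |
| 00:20 | 240 ml lavage | 240 ml lavage |
| 00:50 | TNSS, VAS, PNIF, secretion | TNSS, VAS, PNIF, secretion |
| 00:55 | challenge | challenge |
| 08:30 | secretion, brushing, biopsy | secretion, brushing, biopsy |

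Blood sampling aside, the only difference in what is done to the nose is the 00:15 brushing.

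**Intervals, from the start of the 00:15 slot**

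- Brushing to pre-challenge reading: 00:50 − 00:15 = 35 minutes.
- Brushing to challenge: 00:55 − 00:15 = 40 minutes.
- First to second brushing in controls: 08:30 − 00:15 = 495 minutes.
- Challenge to the only brushing in atopic participants: 08:30 − 00:55 = 455 minutes.

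**Measures taken after the extra brushing**

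- TNSS, VAS and PNIF: all five readings (pre-challenge, 5, 15, 30 and 60 minutes).
- Secretions: six of the day's seven (00:50, 01:00, 01:10, 01:25, 01:55 and 08:30).
- The 08:30 brushing and biopsy.

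**Measures not affected**

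- The 00:15 secretion, provided it is taken before the brushing, which is the order in which the row names them.
- Blood and skin measures.
- Active versus placebo, because both arms follow Table 2.

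**Number of controls affected.** If Table 5 governs, 20 of 20. If the Visit 1 bullets govern, 0 of 20. The SAP schedule of assessments (10.2.1) does not settle it, because as printed it has no column for the non-atopic Visit 1.

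**Size of the effect.** Neither document gives a figure for the effect of brushing or lidocaine on TNSS, PNIF or nasal mediators. The two could act in opposite directions, so no magnitude or sign can be computed.

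**The case against.** The strongest reply is that this is one table row against its own text. The row may be a drafting slip: Tables 1, 3 and 4 give secretion and brushing separate five-minute slots, whereas Table 5 merges them. This stands. A reader might infer from Table 5 that every control was brushed before challenge, but the documents support only that 0 or 20 were scheduled to be, depending on which passage is followed.

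Second, a 240 ml lavage through both nostrils separates the brushing from the 00:50 sample, and may wash out some of what brushing releases. The same sequence is also routine in atopic participants. At Visits 0a and 2 to 5, brushing at 00:20 is followed by lavage at 00:25 and a secretion at 00:55, again 35 minutes later. This stands as a reason not to assert a shift. It does not remove the imbalance, because those visits have no challenge and the 12-month comparison is with Visit 7.

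Third, it is tempting to say that atopic participants are never brushed before a challenge on the same day. The visit schedules read that way, but section 6.6 lists brushings among the screening samples and the screening visit includes a challenge. The Visit -1 procedure list has no brushing, so the point is unsettled. Visit 7 does not depend on it.

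Fourth, the background section gives the controls' purpose as biomarkers in blood, brushings and biopsies, and the protocol's primary endpoint is active versus placebo. Both are true. The SAP nevertheless lists controls in the comparisons of TNSS, PNIF and nasal fluid, and the 08:30 control brushing and biopsy would also come from a nose brushed that morning.

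**Conclusion.** The point holds as an unreconciled schedule that, on one reading, gives the controls an extra procedure before challenge. If Table 5 is followed, all 20 controls differ from the atopic Visit 7 participants on the nasal measures after 00:15, and the three-group nasal comparison at 12 months could be biased to an unknown extent and in an unknown direction. If the visit text is followed, there is no difference.

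Two stronger readings are not supported. A reader might infer that the control values are shifted, but no figure in the documents shows that they are. A reader might also infer that the primary result is compromised, because SAP 7.2.1 lists the three-group comparison under the primary endpoint. Protocol 6.1 and 6.8.3.1 define that endpoint as active versus placebo, and the randomised contrast is untouched.

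The conclusion assumes that Visit 7 is run to Table 2 as its text states. The sparing of the first secretion assumes that it is collected before any brushing in the 00:15 slot.

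**What to change.** **Before the control visits.** Reconcile Table 5 with the Visit 1 text and Table 2 so that the pre-challenge nasal steps match. The simplest way is to remove the brushing from the 00:15 row and keep the one at 08:30. Matching the other way, by adding a morning brushing at Visit 7, would change the conditions of the primary endpoint measurement relative to Visit 0b.

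The cost is one table row and one fewer procedure. The controls lose their only brushing taken before challenge. That sample has no atopic counterpart at Visit 7, although atopic participants do have unchallenged brushings at Visits 0a and 2 to 5.

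**If the control visits are already done.**

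- Report which controls were brushed before challenge and which of them received lidocaine.
- Use the 00:15 secretion for baseline nasal-fluid comparisons where possible.
- Present the comparison of later control nasal measures with that caveat, or with a sensitivity analysis by brushing and lidocaine status if controls differ in either.

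Do not exclude affected controls as a rule. If Table 5 was followed throughout, that would delete the whole non-atopic challenge comparison because of an effect nobody has quantified.

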6.5.15 Study follow up (12-36 months post randomisation)

After 12 months unblinding of the atopic participants will take place. Participants that were included in the active treatment arm (AIT) will continue for a further 24 months follow up. The AIT treatment will be continued for a further 12 months after unblinding (24 months in total). At 24 months (end of treatment, **visit 8**) and at 36 months (12 months after discontinuation, **visit 9**). At visit 8 and 9 all procedures, tests and markers performed at visit 7 (Table 2) will be repeated. Participants who received 12 months placebo will be offered 24 months of active AIT following the unblinding; they will not undergo further investigational assessments.

6.6 Biomarkers

We will measure known and novel biomarkers locally in the nasal mucosa, and in peripheral blood. In atopic participants blood, nasal fluid and nasal brushings will be sampled at screening, baseline, after 4, 8 and 16 weeks and at 7 and 12 months of treatment. The same sampling will be repeated at 24 and 36 months of the open label follow-up for the treatment group. Biopsies will be performed at baseline and at 7 and 12 months of treatment, and at 24 and 36 months of open label follow-up. At screening, 20 ml of blood (10 ml blood count, and 10 ml IgE to timothy grass) will be taken. At baseline, after 4, 8 and 16 weeks, 120 ml blood will be taken (100 ml for T-, B- and dendritic cell (DC) studies and 20 ml for T- and B-cell repertoire analysis). At 7, 12 and at 24 and 36 months, 200 ml will be taken (150 ml for T-, B- and DC studies and 50 ml for T- and B-cell repertoire analysis). The healthy, non-atopic participants will present themselves after screening only once coinciding with Visit 7 at 12 months of the atopic participants. During this assessment 200 ml of blood will be taken (150 ml for T-, B- and DC-studies and 50 ml for T- and B-cell repertoire analysis). Additionally,

nasal fluid, nasal brushings and nasal biopsies will be collected. Different analyses will be performed as described below.

6.6.1 Flow Cytometry

Flow cytometry for analysis of basophils will be performed on fresh blood samples, on the same day as venesection. All other flow cytometry will be performed on stored peripheral blood mononuclear cells (PBMCs), isolated from whole blood by layering over a Ficoll cushion, centrifuging and harvesting the buffy coat layer. PBMCs will be stored at -80°C before thawing and analysis in batches to reduce variability.

6.6.2 DNA Methylation Studies

Regulatory T cells (Tregs) have been implicated in preventing allergic responses. These cells may express the transcription factor FOXP3, the expression of which may be controlled by DNA methylation²². Demethylation at a highly conserved region within the FOXP3 gene was found to be restricted to natural Tregs when tested against all major peripheral blood types and a selection of non-blood cells^{23, 24}. For this study, we intend to use a commercial quantitative real-time PCR-based methylation assay to enable the specific and sensitive determination of Treg numbers by measuring demethylated FOXP3 (e.g. Epionits GmbH, www.epiontis.com). By using the same technology to quantify CD3 positive cells, it is possible to calculate Tregs as a percentage of total T cells.

6.6.3 T-cell Assays

Assays will be performed on thawed PBMCs. 3H-thymidine incorporation and/or carboxy fluorescein succinimidyl ester (CFSE) dilution will be used as a measure of proliferation in response to allergen. Flow cytometry with surface ± intracellular markers will be used to assess T-cell phenotype, to include Th1, Th2 and Treg cells. T-cell function *in vitro* will be assessed by specific ELISA (enzyme linked immunosorbant assay) for cytokines including interleukin-10 (IL-10) and IL-35, and/or by Fluorospot plate assays for IL-4/IL-10 and IL-5/IFN-γ.

